9.3 Variables

The following demographic characteristics will be assessed in the study population:

- Age at index date (in years, categorized, mean (\pm SD), median (IQR))
- History available prior to the index date (in years, categorized, mean (\pm SD), median (IQR))
- Follow-up available after the index date (in months, categorized, mean (\pm SD), median (IQR))

Prescriptions of CPA/EE from index date until end of follow-up will be converted into treatment episodes of uninterrupted use (see section 9.3.1). For hormonal contraceptives this will be done from one year preceding the index date until end of follow-up. ATC and Gemscript codes of hormonal contraceptives are displayed in Table 16.1 and Table 16.2 of Annex 1.

The following CPA/EE treatment characteristics will be assessed at index date:

- Type of CPA/EE (Diane 35 or generic)
- Prescriber (GP, dermatologist, gynaecologist, other specialist, unknown)

NOTE: Distinction between prescriber is only available in PHARMO. In THIN and HSD all prescriptions come from GPs. There are no prescriptions from specialists, but prescriptions may be started by specialists (not captured) and subsequently continued by the GP.

The following CPA/EE treatment characteristics will be assessed from index date until end of follow-up:

- Number of treatment episodes (categorized, mean (\pm SD), median (IQR))
- Summed duration of CPA/EE use (in months, categorized, mean (\pm SD), median (IQR))
- Concomitant use of hormonal contraceptives (concomitant, potential concomitant, non-concomitant or no use of hormonal contraceptives)
- Duration of concomitant use of CPA/EE and hormonal contraceptives (≤ 28 days concomitant use, $>28 - 84$ days concomitant use or >84 days concomitant use, mean (\pm SD), median (IQR))
- Duration of potential concomitant use of CPA/EE and hormonal contraceptives (≤ 28 days potential concomitant use, $>28 - 84$ days potential concomitant use or >84 days potential concomitant use, mean (\pm SD), median (IQR))

Prior treatment of acne, according to European treatment guidelines², will be assessed in the year prior to the index date (index date – 365 days, excluding index date; for included product names and ATC codes see Table 16.3 and Table 16.4 in Annex 2). Acne treatments will be classified as topicals, systemic preparations and hormonal agents and assessed separately for patients with and without an acne diagnoses in the year prior to index date. Because many of the drugs in the tables are not specific for acne, a pragmatic approach will be taken to select actual acne treatment in the study population: 1) select drugs by ATC or Gemscript code; 2) define dose and route of administration; 3) check with local guidelines for the approved indication of use and only include drugs that are approved for acne (alternative indications may exist). This check with the local guidelines is efficient because only the drugs that are actually used in the study population have to be checked once this data is available. Acne treatments will be further classified to whether it is only approved for acne, or also approved for other indications to allow sensitivity analysis.

Prior diagnoses of hyperandrogenic conditions or medical conditions where EE/progestin combinations are prescribed for frequently will be assessed in the year prior to index date (index date – 365 days, excluding index date; for included codes, see Table 16.5 and Table 16.6):

- Acne
- Alopecia
- Contraceptive management
- Hirsutism
- Menstrual problems
- Oligomenorrhoea/amenorrhoea
- Polycystic ovary syndrome (PCOS)
- Seborrhoea

For the 2017 study extension the following will be assessed:

Demographic characteristics:

- Age at index date (in years, categorized, mean (\pm SD), median (IQR))
- History available prior to the index date (in years, categorized, mean (\pm SD), median (IQR))
- Follow-up available after the index date (in months, categorized, mean (\pm SD), median (IQR))

Concomitant use of hormonal contraceptives:

- Number of CPA/EE treatment episodes (categorized, mean (\pm SD), median (IQR))
- Summed duration of CPA/EE use (in months, categorized, mean (\pm SD), median (IQR))
- Concomitant use of hormonal contraceptives (concomitant, potential concomitant, non-concomitant or no use of hormonal contraceptives)
- Duration of concomitant use of CPA/EE and hormonal contraceptives (≤ 28 days concomitant use, $>28 - 84$ days concomitant use or >84 days concomitant use, mean (\pm SD), median (IQR))
- Duration of potential concomitant use of CPA/EE and hormonal contraceptives (≤ 28 days potential concomitant use, $>28 - 84$ days potential concomitant use or >84 days potential concomitant use, mean (\pm SD), median (IQR))

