9.3.1 Episodes of CPA/EE and hormonal contraceptive use

The duration of each CPA/EE and hormonal contraceptive prescription will include the medication-free days, if applicable. For CPA/EE, which is dosed in cycles of 21 days on medication and a 7-day interval without medication, the duration of one blister pack will thus be 28 days and the duration of a prescription will be the duration of one blister pack * the number of blister packs prescribed (see Figure 9.1). Most (if not all) oral hormonal contraceptives, patches and rings are also dosed in 28-day cycles with variations in the number of medication-free days. For intra-uterine devices, injections and implants the duration will be defined as the duration of effectiveness or until removal of the intra-uterine devices or implant when this is identified in the database. For each hormonal contraceptive the duration of effectiveness will be defined from the label.

Subsequent prescriptions of the same drug will be concatenated if the new prescription date precedes the end date of the previous prescription. The adjusted start date of the new prescription will be the day after the end date of the previous prescription. Subsequently, prescriptions of CPA/EE and hormonal contraceptives between index date – 365 days and end of follow-up will be converted into treatment episodes of uninterrupted use. In case of an interruption between two prescriptions, use of the drug will be considered interrupted and the treatment episode ends, i.e. no gap is allowed between two prescriptions.

Patients may have several treatment episodes of CPA/EE and hormonal contraceptives after treatment onset.

[figure not shown]

Figure 9.1 Cycles, prescriptions and treatment episodes of CPA/EE and hormonal contraceptives

Each box indicates one cycle, e.g. a blister pack. Subsequent cycles constitute a prescription, and subsequent prescriptions constitute a treatment episode.

9.3.2 Definition of switching and (potential) concomitant use of CPA/EE and hormonal contraceptives

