Switching between hormonal contraceptives will be defined as a prescription date of a new hormonal contraceptive preceding the end date of a previous episode of another hormonal contraceptive. As most hormonal contraceptives are given in cycles, the assumption will be that the user will finish a cycle (e.g. the blister pack or patch) of the first hormonal contraceptive before starting a new one. Hence, the adjusted end date of the previous episode will be the end date of the cycle during which the new prescription was observed. The adjusted start date of the new hormonal contraceptive will be the day after the adjusted end date of the previous.

If the previous contraceptive is not given in cycles (e.g. progestogen-only pills, intra-uterine devices, implants) the adjusted end date will be the day before the date of the new prescription and the start date of the new hormonal contraceptive will not be adjusted.

For all episodes of CPA/EE, overlap with hormonal contraceptive episodes will be assessed similarly to the switches between hormonal contraceptives. However, as concomitant use of CPA/EE and hormonal contraceptives is among the study objectives, we will not define a switch but classify in terms of (potential) concomitant use. The days between the adjusted end date and the original end date of a truncated episode will be classified as:

- Potential concomitant use: (see Figure 9.2) when a “switch” from CPA/EE to a hormonal contraceptive *or vice versa* occurs during the last prescription within a treatment episode
- Concomitant use: when both start and end date of a hormonal contraceptive episode lie between start and end date of a CPA/EE episode *or vice versa*; or when a “switch” from CPA/EE to a hormonal contraceptive *or vice versa* precedes the last prescription within a treatment episode.
- Non-concomitant use: both start and end date of a hormonal contraceptive episode lie outside a CPA/EE episode (i.e. before or after both start and end date of a CPA/EE episode).
- No use of hormonal contraceptives (no observed treatment episodes of hormonal contraceptives within 365 days before the index date until end of follow-up).

Because the validity of estimating duration differs between administration routes (oral, intra-uterine, implant, injection, ring and patch) concomitant use will be computed separately and presented separately in text or tables, depending on the numbers observed.

[figure not shown]

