9.9 Limitations of the research methods

Drug utilization studies conducted in automated healthcare databases allow identification of patients who are prescribed or dispensed the drugs of interest and characterisation of these patients according to prior medical history, use of medications, and patterns of use of medications. Healthcare databases have become a useful tool for conducting research to study the safety of drugs as information on diagnoses and treatments is recorded on an ongoing basis.

Limitations regarding treatment

Healthcare databases are used as administration tools in patient care and have their limitations with regard to their use in scientific research, mainly related to the type and completeness of the recorded information. Regarding treatment data, databases provide detailed information on prescribed and/or dispensed medications but not on the actual use of the medications by patients. Thus, patients may be classified as exposed when they are not actually taking the drug. Furthermore, databases often do not record the intended duration of use of each prescription (days of supply). This needs to be estimated from the interval between consecutive prescriptions and can result in misclassification of drug exposure. In particular the use of long-acting hormonal contraceptives (intra-uterine devices, injections and implants) may be misclassified. To be eligible for inclusion in our study, women were requested to have at least one year enrolled with the general practitioner, this eligibility criterion may result into some misclassification of exposure of these devices in both directions, potential for false negatives (underecorded use (earlier the year prior index date) or false positivies (removal or ended life cycle of these devices at the time of index date or during the year after). However, we expect the use of LARC to be low in this population, as women initiating CPA are expected to be on average 20-23 years old⁷. As the indication of use is not recorded for most of the prescriptions, the identification of the indication depends on concomitantly recorded diagnoses. Another limitation of the assessment of medication use from databases is that over-the-counter medications are usually not recorded. As OTC medications do play an important role in the treatment of acne the limitation of not recording those needs to be taken into consideration when interpreting the results. Furthermore, as discussed in

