15.1 Patient selection and characteristics

15.1.1 Patient selection and characteristics in PHARMO

[figure not shown]

Figure 15.1 Flow chart of patient selection in PHARMO

NOTE: this flow chart will be repeated for each database. An additional level of ‘GP data available’ will be added for PHARMO

Table 15.1 General characteristics of new CPA/EE users in PHARMO per calendar year

| | 2011 starters N=7,876 n (%) | 2012 starters N=7,562 n (%) | 2014 starters N=1,401 n (%) | 2015 starters N=0,000 n (%) | 2016 starters N=0,000 n (%) | 2017 starters N=0,000 n (%) |
|---|--|--|--|--|--|--|
| Age (years) | | | | | | |
| <15 | 278 (4) | 262 (3) | 13 (1) | | | |
| 15-<25 | 3,986 (51) | 3,733 (49) | 482 (34) | | | |
| 25-<35 | 2,385 (30) | 2,365 (31) | 584 (42) | | | |
| 35-<45 | 1,001 (13) | 968 (13) | 242 (17) | | | |
| 45-<55 | 211 (3) | 229 (3) | 73 (5) | | | |
| ≥55 | 15 (<0.5) | 5 (<0.5) | 7 (<0.5) | | | |
| mean ± SD | 25 ± 9 | 25 ± 9 | 29 ± 9 | | | |
| median (IQR) | 23 (18-31) | 24 (18-31) | 27 (23-34) | | | |
| Database history before index date (years) | | | | | | |
| 1-<2 | 420 (5) | 418 (6) | 91 (6) | | | |
| 2-4 | 966 (12) | 648 (9) | 140 (10) | | | |
| >4 | 6,490(82) | 6,496 (86) | 1,170 (84) | | | |
| mean ± SD | 8 ± 4 | 9 ± 4 | 9 ± 5 | | | |
| median (IQR) | 7 (5-12) | 8 (6-13) | 9 (6-11) | | | |
| Follow-up after index date (months)* | | | | | | |
| <6 | 3,877 (49) | 3,573 (47) | 641 (46) | | | |
| 6-12 | 3,999 (51) | 3,989 (53) | 760 (54) | | | |
| mean ± SD | 6 ± 3 | 6 ± 3 | 6 ± 3 | | | |
| median (IQR) | 6 (3-9) | 6 (3-9) | 6 (3-9) | | | |

* by definition, the follow-up will not be longer than 12 months (see section 9.2).

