15.1.3 Patient selection and characteristics in HSD

[figure not shown]

Figure 15.3 Flow chart of patient selection in HSD

Table 15.3 General characteristics of new CPA/EE users in HSD per calendar year

| | 2011 starters N=495 n (%) | 2012 starters N=446 n (%) | 2014 starters N=261 n (%) | 2015 starters N=0,000 n (%) | 2016 starters N=0,000 n (%) | 2017 starters N=0,000 n (%) |
|---|--|--|--|--|--|--|
| Age (years) | | | | | | |
| <15 | 5 (1) | 0 (0) | 1 (<0.5) | | | |
| 15-<25 | 207 (42) | 212 (48) | 105 (40) | | | |
| 25-<35 | 146 (29) | 120 (27) | 83 (32) | | | |
| 35-<45 | 93 (19) | 71 (16) | 47 (18) | | | |
| 45-<55 | 36 (7) | 33 (7) | 19 (7) | | | |
| ≥55 | 8 (2) | 10 (2) | 6 (2) | | | |
| mean ± SD | 29 ± 10 | 29 ± 10 | 29 ± 11 | | | |
| median (IQR) | 26 (21-36) | 25 (21-35) | 26 (21-36) | | | |
| Database history before index date (years) | | | | | | |
| 1-<2 | 18 (4) | 14 (3) | 11 (4) | | | |
| 2-4 | 41 (8) | 36 (8) | 27 (10) | | | |
| >4 | 436 (88) | 396 (89) | 223 (85) | | | |
| mean ± SD | 11 ± 7 | 11 ± 6 | 12 ± 7 | | | |
| median (IQR) | 11 (6-15) | 11 (7-15) | 12 (7-16) | | | |
| Follow-up after index date (months)* | | | | | | |
| <6 | 232 (47) | 224 (50) | 118 (45) | | | |
| 6-12 | 263 (53) | 222 (50) | 143 (55) | | | |
| mean ± SD | 6 ± 4 | 6 ± 4 | 6 ± 4 | | | |
| median (IQR) | 6 (3-9) | 6 (3-9) | 7 (3-10) | | | |

* by definition, the follow-up will not be longer than 12 months (see section 9.2).

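### The one-year look-back generally misses implants and intra-uterine systems placed earlier but still active at index, and section 9.9 names the wrong cause

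*Protocol*

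**What the plan says.** Four parts of the protocol bear on this point.

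- **Window.** Section 9.3, on contraceptive episodes: "For hormonal contraceptives this will be done from one year preceding the index date until end of follow-up". Section 9.3.1 repeats it: "prescriptions of CPA/EE and hormonal contraceptives between index date – 365 days and end of follow-up will be converted into treatment episodes of uninterrupted use".
- **Duration.** Also in section 9.3.1: "For intra-uterine devices, injections and implants the duration will be defined as the duration of effectiveness or until removal", where a removal can be identified. The duration is to come from the label; no number of years is given.
- **No-use category.** Section 9.3.2 defines it as "no observed treatment episodes of hormonal contraceptives within 365 days before the index date until end of follow-up".
- **Disclosure.** Section 9.9 warns that long-acting methods may be misclassified, with false negatives from earlier use and false positives from devices removed or expired. It ascribes this to the requirement of one year's enrolment, and expects little such use because "women initiating CPA are expected to be on average 20-23 years old".

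The abstract (section 4) puts implants and intra-uterine devices in scope. Section 9.2 makes 365 days of recorded history a minimum for inclusion. Tables 15.1 to 15.3 already hold the history and ages of the 2011, 2012 and 2014 cohorts. The mean-age row for HSD, for example, reads "29 ± 10 | 29 ± 10 | 29 ± 11".

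**The concern.** The duration rule and the look-back rule do not fit together. A device placed 18 months before index, with a labelled life of several years, is still active when CPA/EE starts. Its insertion record lies outside the window, so no episode is formed. If the woman has another contraceptive record in the window, she is classed on that record and the device is still missed. If she has none, she is reported as not using hormonal contraception.

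Overlap between CPA/EE and hormonal contraceptives is the safety question behind the study (section 7), and its trend over 2011-2017 is an objective of the extension (section 8.2). Section 9.3.2 also promises results by administration route, which is where such misses would be concentrated.

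The protocol accepts the underlying logic elsewhere. For PHARMO, section 9.2 and Table 5.1 (deviation 1) treat a CPA/EE prescription issued more than a year before index as prior use if it expired within that year. No comparable rule is given for the contraceptive methods that last longest.

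**Working it through.** **1. Is one year all the history there is?** Women with more than 4 years of history, divided by cohort size, from Tables 15.1 to 15.3:

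| Database | 2011 | 2012 | 2014 |
|---|---|---|---|
| PHARMO | 6,490/7,876 = 82.4% | 6,496/7,562 = 85.9% | 1,170/1,401 = 83.5% |
| THIN | 2,341/2,760 = 84.8% | 2,481/2,923 = 84.9% | 1,999/2,341 = 85.4% |
| HSD | 436/495 = 88.1% | 396/446 = 88.8% | 223/261 = 85.4% |

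Pooled: 22,032/26,065 = 84.5%. The three history categories add up to N in all nine cohorts. Eight of the nine printed percentages agree on rounding; THIN 2011 prints 84 where the counts give 84.8%, which is immaterial. The 2015-2017 columns are empty, so the result covers the completed cohorts only. For most women, then, the limit is the chosen window and not the data held.

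**2. Does the age argument fit?** Section 9.9 expects an average of 20 to 23 years. The tables show:

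| Database | Mean age 2011 / 2012 / 2014 | Median age | Aged 25 or over |
|---|---|---|---|
| PHARMO | 25 / 25 / 29 | 23 / 24 / 27 | 45.9 / 47.2 / 64.7% |
| THIN | 23 / 23 / 23 | 22 / 22 / 22 | 39.3 / 38.7 / 38.2% |
| HSD | 29 / 29 / 29 | 26 / 25 / 26 | 57.2 / 52.5 / 59.4% |

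The last column is 1 minus the two youngest age groups over N; for PHARMO 2014, 1 − (13 + 482)/1,401 = 64.7%. On means, only THIN fits. On medians, PHARMO 2011 also fits and PHARMO 2012 is one year above; PHARMO 2014 and all HSD cohorts lie above the range.

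**3. What share of devices in place at index would a 365-day window miss?** The protocol gives neither device lives nor removal rates, so these are assumptions: steady insertion over time, labelled life D of 3 or 5 years, and constant annual removal r from 0% to 30%. Devices in place at index with age up to t are proportional to S(t), the integral of (1 − r)^a from 0 to t. For r = 0, S(t) = t. For r > 0, S(t) is proportional to 1 − (1 − r)^t.

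Missed share = 1 − S(1)/S(D):

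- D = 3, r = 0: 1 − 1/3 = 66.7%
- D = 3, r = 30%: 1 − 0.30/(1 − 0.343) = 54.3%
- D = 5, r = 0: 1 − 1/5 = 80.0%
- D = 5, r = 30%: 1 − 0.30/(1 − 0.168) = 63.9%

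**4. What would a longer look-back change?** With 4 years of look-back the missed share is 1 − S(min(4, D))/S(D):

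- D = 3: 0%
- D = 5, r = 0: 1 − 4/5 = 20.0%
- D = 5, r = 30%: 1 − (1 − 0.240)/(1 − 0.168) = 8.7%

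This applies to the 82% to 89% of women with more than 4 years of history, and assumes that every insertion is recorded.

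**5. What cannot be computed.** These are shares of devices, not of women. Turning them into a change in the no-use or concomitant percentages needs the prevalence of long-acting methods among CPA/EE starters, which the protocol does not give.

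**The case against.** The strongest reply is that the limitation is already disclosed, in both directions, and that the regulator asked for the same methodology so that years can be compared (Table 5.1, item 6). Both points are right. They argue against replacing the main definition, but not against a parallel analysis. Disclosure also does not settle the matter when its two explanations do not match the protocol's own tables.

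Several stronger readings are tempting and are not supported.

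- **That older devices are never seen.** Table 16.2 includes THIN codes for an implant in situ, an implant check and a coil check; any of these in the window can reveal an older device. Table 5.1 (deviation 5) says THIN assessed overlap before index from contraceptive prescriptions, with no look-back limit stated. The gap is therefore mainly in PHARMO and HSD.
- **That concomitant use is biased downward on balance, or that the trend is distorted.** Missed devices lower the count, but unrecorded removals raise it, and no prevalence is given. The share aged 25 or over rises clearly only in PHARMO; it is flat in THIN and uneven in HSD.
- **That a full look-back recovers every device.** Recording is incomplete: THIN lacks family planning clinics (section 9.4.2), HSD does not capture contraceptives exhaustively (section 9.4.3), and GP databases lack specialist prescriptions (section 9.9). Removal codes are listed for THIN only; Table 16.1, for PHARMO and HSD, lists product codes alone. Where removals cannot be found, older devices would run to their labelled end and add false positives.
- **That injections share the problem.** The calculation concerns multi-year devices, and nothing shown extends it to injections.

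**Conclusion.** The point holds in limited form. Implants and intra-uterine systems placed more than a year before index and still active generally form no episode, mainly in PHARMO and HSD. The cause of these false negatives is the chosen window and not the enrolment minimum, since 82% to 89% of women in each completed cohort have more than 4 years of history. The age argument in section 9.9 fits THIN, but not the mean ages in PHARMO or HSD.

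Under the stated assumptions on device life, insertion and removal, the window misses about 54% to 80% of devices in place at index. The absolute effect on concomitant use and on its trend is unknown and may be small. A reader might infer that the main safety result is materially understated; the protocol contains nothing that would show this. The gap is avoidable and cheap to examine, and does not invalidate the main analysis.

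**What to change.** - Keep the current definition as the main analysis, so that the extension stays comparable with the earlier report.
- Add a sensitivity analysis in each database for all six years (2011, 2012, 2014, 2015, 2016, 2017). For implants and intra-uterine systems only, search all available history before index, start the episode at insertion, and end it at recorded removal, replacement or the end of labelled effectiveness. Leave injections, pills, rings and patches as they are. Report by route, next to the main result.
- State that unrecorded removals can add false positives, especially in PHARMO and HSD where no removal codes are listed, and that women with short history are covered less fully. The two definitions should be read together.
- Correct section 9.9 to name the look-back window as the cause of the false negatives, and replace the 20-to-23-year expectation with the ages in Tables 15.1 to 15.3.

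The cost is a wider extraction window for a short code list, a rerun of the completed cohorts and additional table rows. No new data source is needed.

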Table 5.1 Amendments and updates to the Study Protocol

| Number | Date | Section of Study Protocol | Amendment or update | Reason |
|---------------|---------------|---|---|--|
| 1 | 30 March 2015 | 9.2 Setting | A prescription of CPA/EE in the year prior to index date was an exclusion criterion. In PHARMO, users were excluded as prevalent also when the prescription was more than one year prior to the index date but expired less than one year before the index date. | Exclusion of these women was more accurate. |
| 2 | 30 March 2015 | 9.2 Setting | In the Study Protocol an analysis of 2011/2012 was planned as well as an analysis of 2011 and 2012 separately. In the study report, only the calendar year analysis is presented. | The difference in recruitment periods between the analyses was confusing and the results in the analyses were similar. As the comparison of the 2014 analysis will be with the calendar years cohorts, it was decided to only present these. |
| 3 | 29 May 2015 | 9.2 Setting | PHARMO and HSD users who were new users in 2011 as well as in 2012, i.e. were using CPA/EE for a short time in 2011 and re-started after more than 365 days in 2012, were included in both populations. In THIN the 365-day period was applied before the date of study period entry, i.e. before Jan 1, 2011. By definition no users could re-enter in 2012. | At CEIFE standard procedure is to apply the medication-free period to the time before entry date rather than the index date. In practice this leads to only very small differences in numbers of users selected. |
| 4 | 29 May 2015 | 9.3 Variables | The index date was included in the assessment of diagnoses of acne and other hyperandrogenic conditions. | Extending the time window up to the index date also included the diagnoses recorded on the date of CPA/EE prescription, i.e. the likely indication of use. |
| 5 | 19 June 2015 | 9.3.2 Definition of switching and (potential) concomitant use of CPA/EE and hormonal contraceptives | In THIN, HC episodes were only created after the index date, not before. Overlap between other HC and CPA/EE before index date was assessed examining overlap between HC prescriptions and the first CPA/EE episode. | Different interpretation of the Study Protocol and different local standard programs. |

Table 5.1 Amendments and updates to the Study Protocol

| Number | Date | Section of Study Protocol | Amendment or update | Reason |
|--------|------------|---------------------------------|---|---|

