9.2 Setting

The study population will include all individuals registered in the databases receiving CPA/EE (ATC G03HB01) and Gemscript codes (85864998, 86466998, 86925998, 87351998, 90826979, 91068998, 91069998, 94832990, 94913992, 94920998, 95396990, 96577998 and 97520998) between January 1, 2011 and December 31, 2012 (study period for the first run) or January 1, 2014 and December 31, 2014 (study period for the second run). The year 2013 is not included in the identification period, as this is the year in which changes in policies and recommendations for CPA/EE usage have been implemented. The date of receiving the first prescription of CPA/EE in the study period will be defined as the index date.

The annual study periods for the 2017 extension will be between January 1 and December 31 of 2015, 2016 and 2017, respectively.

Exclusion criteria are:

- Men
- <365 days recorded history in the database prior to index date
- Use of CPA/EE in the year prior to the index date, defined by
 - a prescription of CPA/EE in the year prior to index date, or
 - a prescription of CPA/EE in the year prior to entry date (start of the study period or database entry, whichever occurred first) (THIN only, see Table 5.1 deviation #3) or
 - expiration of a prescription of CPA/EE in the year prior to index date (PHARMO only, see Table 5.1 deviation #1)

Patients will be followed from index date to transfer out of the database (end of follow-up available/censoring), end of study period, whichever occurs first. The first run will include an overall analysis (2011-2012) and an analysis by calendar year (2011 and 2012), for which separate recruitments will be performed (i.e. summing patients from the analysis by calendar year 2011 and 2012 may give a higher number than for the overall analysis). In the analysis by calendar year the end of the study period will be defined as December 31 of the year of index date (December 31, 2011, December 31, 2012).

For the 2017 study extension an analysis by calendar years will be performed..

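### As written, Section 9.3 stops the diagnosis window the day before the first CPA/EE prescription, so a diagnosis coded only on that day is not counted, against the reasoning in 9.9 and Table 5.1 entry 4

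*Protocol*

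**What the plan says.** Section 9.2 fixes day 0: "The date of receiving the first prescription of CPA/EE in the study period will be defined as the index date".

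Section 9.3 then sets two look-back windows, both running from 365 days before the index date and both leaving that date out. One is for prior acne treatment. The other is for eight groups of prior diagnoses: acne, alopecia, contraceptive management, hirsutism, menstrual problems, oligomenorrhoea/amenorrhoea, PCOS and seborrhoea. For the diagnoses the wording is "excluding index date; for included codes, see Table 16.5 and Table 16.6". Acne treatment is also to be "assessed separately for patients with and without an acne diagnoses in the year prior to index date", which is the split shown in Tables 14.5 and 14.6.

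Section 9.9 explains how the reason for prescribing is to be found: "As the indication of use is not recorded for most of the prescriptions, the identification of the indication depends on concomitantly recorded diagnoses".

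Table 5.1 entry 4, dated 29 May 2015 and assigned to Section 9.3, records: "The index date was included in the assessment of diagnoses of acne and other hyperandrogenic conditions". The reason given is that the longer window "also included the diagnoses recorded on the date of CPA/EE prescription, i.e. the likely indication of use".

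**The concern.** Leaving out the index date suits prior treatment, because a treatment tried before CPA/EE should precede it. That reason does not carry over to diagnoses. The code entered when CPA/EE is first prescribed is the one most likely to state why it was prescribed, and a window ending on day -1 discards it unless the same condition was also coded in the preceding year.

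Previous diagnosis is one of the main objectives in Section 8.1, and Section 7 describes use as restricted to moderate to severe acne and/or hirsutism. An analyst who follows 9.3 would report too few women with a recorded diagnosis in Tables 14.7 and 14.8. In Tables 14.5 and 14.6, women whose acne was first coded on the index date would fall among those without an acne diagnosis, and any acne treatment they had received would appear there too.

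**Working it through.** There is no figure in the plan to reproduce. The check is a comparison of texts.

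1. **Window in 9.3, read literally:** days -365 to -1. Day 0 is the first CPA/EE prescription (9.2).
2. **Window in Table 5.1 entry 4:** days -365 to 0.
3. **What differs:** a woman is classified differently only if she has a relevant code on day 0 and none on days -365 to -1. Everyone else is classified alike under both windows.
4. **Direction:** the literal window lies inside the other, so for each diagnosis the count under 9.3 is less than or equal to the count under entry 4. If P is the proportion with the diagnosis over days -365 to 0, and s is the share of those women coded on day 0 only, the 9.3 rule reports P × (1 - s). The loss is P × s, and it moves to the group without that diagnosis. The documents give neither P nor s.
5. **Against 9.9:** that section relies on diagnoses recorded concomitantly with the prescription. A same-day code is the clearest example, and 9.3 omits it.
6. **Were the log entries carried into the body?** Deviations #1 and #3 were written into 9.2 as operative rules with a pointer, for example "expiration of a prescription of CPA/EE in the year prior to index date (PHARMO only, see Table 5.1 deviation #1". Entry 4 has no counterpart in 9.3, neither the change nor a pointer. The abstract and the titles of Tables 14.7 and 14.8 also still refer only to the year before the index date.
7. **Does entry 4 settle everything?** No. It speaks of acne and other hyperandrogenic conditions. It does not say whether contraceptive management and menstrual problems follow the same window, or whether the acne split in Tables 14.5 and 14.6 was changed with it.
8. **By database:** Section 9.4.1 says that a prescription in PHARMO means a dispensing. A diagnosis made at a visit on an earlier day than the dispensing is therefore still inside the 9.3 window. In THIN and HSD all prescriptions come from the GP (9.3), so same-day coding is directly exposed. Even there, 9.3 notes that a specialist may have started treatment, in which case the first GP prescription need not be the diagnostic visit.
9. **By study period:** the extension variables in 9.3 do not include diagnoses, so only the 2011/2012 and 2014 runs are concerned.

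**The case against.** The strongest reply is that the matter has already been dealt with. Table 5.1 works here as a live list of deviations, since 9.2 cites it for operative rules. Entry 4 states in the past tense that the index date was included, and gives the same reason as this point does. A difference between an amendment log and the body is not in itself a fault. This reply stands in part. A reader might infer from 9.3 that the study actually dropped same-day diagnoses; entry 4 says the opposite, so that inference is not supported. The reply does not repair 9.3, however. The point rests on 9.3 against 9.9, and entry 4 only shows that the sponsor accepts the reasoning.

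A second reply is that the objective concerns previous diagnoses, and a window ending on day -1 implements that word. This is a fair literal reading, but it gives up the information that 9.9 depends on.

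A third reply is that 9.9 is a statement of limitations, not a window rule, and leaves the word concomitantly undefined. That is correct as far as it goes. A reader might take 9.9 to say that a same-day code is the only route to the indication. It does not: it says the indication is missing for most prescriptions, and diagnoses from the preceding year also count.

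A fourth reply is that little remains to be changed in practice, because the runs that use diagnoses were due to be reported in March 2016 and the extension does not use them. This limits the practical weight of the point. It still matters that the protocol describe the window behind those tables correctly.

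**Conclusion.** The point holds as a defect in the operative wording of 9.3. Followed as written, the rule can only lower the recorded frequency of each listed diagnosis, and it moves women whose acne was first coded on the index date into the stratum without an acne diagnosis.

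The size cannot be derived. It is confined to women with a code on the index date and none in the preceding 365 days. It is likely smaller in PHARMO, on the assumption that some dispensings fall on a later day than the visit, and it does not reach the 2015-2017 extension.

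Two stronger conclusions are tempting and should not be drawn:

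- **That off-label use is overstated.** The protocol plans no on-label or off-label estimate. The window also omits same-day codes for contraceptive management and menstrual problems, so the effect on any such split is not fixed in direction.
- **That the loss can be given a number.** If P were 50% and s were 20% to 40%, the reported figure would be 50% × 0.8 = 40% down to 50% × 0.6 = 30%. Neither input has any basis in the documents, so this is arithmetic and not an estimate.

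**What to change.** - In 9.3, define the diagnosis window as running from 365 days before the index date up to and including the index date, for all eight diagnosis groups, with a cross-reference to Table 5.1 entry 4 in the way 9.2 refers to deviations #1 and #3.
- State that the same window defines the strata with and without an acne diagnosis in Tables 14.5 and 14.6.
- Bring the abstract and the titles of Tables 14.7 and 14.8 into line. The captions of Tables 16.5 and 16.6 use similar wording and can be changed at the same time.
- Leave the window for prior acne treatment as it is, without the index date.

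The cost is wording only, with no new data. If the acne strata already reported were built on the narrower window, that should be stated beside the tables.
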